### 5.2. Timing of Analyses

The final analysis will be performed after the clinical and non-clinical databases are locked.

### 5.3. Analysis Populations

A tabular listing ([Listing 5](#)) and summary table ([Table 3](#)) of all randomized and enrolled subjects excluded from the Safety Population, PK Analysis Population, or PK Analysis Subset will be included in the abbreviated CSR. Although there may be multiple reasons for exclusion from a PK Analysis Population or PK Analysis Subset, only one reason will be counted when summarizing reasons for exclusion from analysis populations. Priority for assigning reasons for exclusions will follow the order listed in [Table 3](#).

#### 5.3.1. Safety Population

All subjects that received any amount of study product will be included in the Safety Population.

#### 5.3.2. PK Analysis Population

The PK Analysis Population will consist of all subjects who complete one full (as randomized, according to cohort) rezafungin dose and have one post-dose plasma sample with measurable rezafungin. Note that all rezafungin concentration results will be included in listings, including results from placebo subjects.

#### 5.3.3. PK Analysis Subset

The PK Analysis Subset will be a subset of the PK Analysis Population and will include all subjects in the PK Analysis Population who completed the PK part of the trial without any protocol violations that would likely affect the PK results and who have evaluable plasma concentration data for rezafungin from which at least a subset of the designated PK parameters can be determined. The statistician will review protocol deviations to determine a list of recommended exclusions due to protocol deviations likely to affect PK. The principal

investigator will review the list prior to unblinding and provide confirmation of any exclusions of subjects due to protocol deviations.

#### **5.4. Covariates and Subgroups**

The protocol does not define any formal subgroup analyses.

#### **5.5. Missing Data**

No imputation of missing data is planned.

#### **5.6. Interim Analyses and Data Monitoring**

No interim analysis was conducted prior to study termination.

#### **5.7. Multicenter Studies**

This is a single-site study.

#### **5.8. Multiple Comparisons/Multiplicity**

This is a Phase 1 first-in-human study with multiple primary endpoints. Because analyses of primary endpoints are descriptive rather than hypothesis tests, no adjustments for multiple testing are planned

## 6. STUDY SUBJECTS

### 6.1. Disposition of Subjects

Screened subjects who were ineligible for enrollment in the study (screen failures) or eligible but not enrolled will be summarized by inclusion and exclusion criteria ([Table 4](#)). Enrolled subjects who were ineligible for inclusion in analysis populations will be summarized by reason for subject exclusion and Dose Group ([Table 3](#)). Individual subject listings of subjects who were excluded from the Safety Population or a PK Analysis Population will be listed ([Listing 5](#)).

Subject disposition will be summarized ([Table 2](#)), showing the number of subjects who screened, enrolled, received study product, completed all PK blood draws, completed final study visit, and early termination.

Subjects who discontinued dosing or terminated early from the study will be listed ([Listing 2](#)).

A flowchart showing the disposition of study subjects will be included ([Figure 1](#)). This figure will present the number of subjects screened, enrolled, lost to follow-up, and analyzed, by Dose Group.

### 6.2. Protocol Deviations

A summary of protocol deviations will be presented by deviation category, deviation type, and Dose Group ([Table 1](#)). This table will provide both the number of subjects and the number of deviations for each category. All subject-specific protocol deviations and non-subject-specific protocol deviations will be listed ([Listing 3](#) and [Listing 4](#)).

## 7. SAFETY EVALUATION

All safety analyses will be performed using the Safety Population.

Any medical condition that is present at the time that the subject is screened will be considered baseline and not reported as an AE unless it worsens in severity or increases in frequency during the study. The denominators for percent values will be indicated within the table or table header and denoted as N. Moreover, events summarized by subject will be coded to the highest severity observed over the indicated time period. Toxicity grading scales for adverse events, solicited reactogenicity symptoms, safety labs, VS, and ECG are provided in the protocol v6.0.

### 7.1. Demographic and Other Baseline Characteristics

Demographic summaries will include all subjects that were randomized. Sex, ethnicity, and race of all subjects will be summarized categorically by Dose Group ([Table 5](#)). Age at enrollment and height, weight, and BMI at screening will be summarized as continuous variables by Dose Group ([Table 6](#)). Individual subject listings will be presented for all demographic and baseline characteristics ([Listing 6](#)).

#### 7.1.1. Prior and Concurrent Medical Conditions

All current illnesses and past pre-existing medical conditions will be MedDRA coded using MedDRA dictionary version 23.0 or higher. Summaries of subjects' pre-existing medical conditions by MedDRA system organ class (SOC) will be presented by Dose Group ([Table 7](#)). Individual subject listings will be presented for all medical conditions ([Listing 7](#)).

#### 7.1.2. Prior and Concomitant Medications

All medications will be coded using the current version of the WHO Drug dictionary. The use of prior and concomitant medications taken during the study will be summarized by Anatomical Therapeutic Code (ATC) 1 and ATC 2 (separately in [Table 33](#) for prior medications and [Table 34](#) for concomitant medications). Individual subject listings will be presented for all prior and concomitant medications (separately in [Listing 23](#) for prior medications and [Listing 24](#) for concomitant medications).

### 7.2. Measurements of Treatment Compliance

Date and time of dosing will be presented in [Listing 8](#). Concentration in plasma for Cohort 2 (including placebo) will be presented in [Listing 31](#).

### 7.3. Adverse Events

When calculating the proportions of subjects with AEs within a given MedDRA category, each subject will only be counted once and any repetitions of AEs within a subject will be ignored, and the event will be reported according to the worst severity recorded (separately for related and unrelated AEs, when both severity and relatedness are tabulated).

#### 7.3.1. Solicited Reactogenicity Symptoms

For each solicited local reactogenicity symptom, the number and percentage of subjects reporting each symptom will be summarized by maximum severity for a specified time point and Dose Group.

Maximum severity for each symptom based on functional grading and measurement grading criteria as described in protocol v6.0 will be summarized separately. All pre-dose and post-dose solicited local reactogenicity will be presented in [Listing 9](#).

The following summaries for solicited local reactogenicity symptoms will be presented:

- The number and proportion of subjects with local symptoms, summarized by Dose Group and symptom. A 95% CI will be presented by Dose Group for each local symptom ([Table 9](#)).
- The number and proportion of subjects with local symptoms, summarized by Dose Group, symptom, and maximum severity. A 95% CI will be presented by Dose Group for each local symptom ([Table 10](#)).
- The number and proportion of subjects with local symptoms, summarized by Dose Group, symptom, time point, and maximum severity (including maximum severity post-baseline) ([Table 11](#)).
- By Dose Group, bar charts of proportions of subjects with local symptoms by maximum severity (each subject counted once per symptom) ([Figure 2](#)).
- By Dose Group and time point, bar charts of proportions of subjects with each local symptom by maximum severity (starting at [Figure 3](#), continuing through [Figure 16](#)).

The following solicited local reactogenicity symptoms will be presented (in order):

- Pain, tenderness, pruritus (itching), ecchymosis (bruising) (functional grade), ecchymosis (bruising) (measurement grade), induration (hardness)/ swelling (functional grade), induration (hardness)/ swelling, (measurement grade), erythema (redness) (functional grade), erythema (redness) (measurement grade), nodule (functional grade), nodule (measurement grade), ulceration (functional grade), and ulceration (measurement grade).

### 7.3.2. Unsolicited Adverse Events

A brief overall summary of AEs by Dose Group including number of subjects with at least one solicited reactogenicity event of any severity, number of subjects with ulceration, number of subjects with at least one AE of any severity, number of subjects with at least one related AE of any severity, and number of subjects with at least one SAE ([Table 8](#)).

All AEs will be presented in listings ([Listing 10](#)). A subject listing of non-serious AEs of moderate or greater severity will also be reported ([Table 15](#)).

The following summaries for unsolicited adverse events will be presented:

- The total number of AEs and the number and proportion of subjects reporting at least one unsolicited AE will be summarized by Dose Group, SOC, and PT. Denominators for percentages are the number of subjects in the Safety Population. A 95% CI will be presented by Dose Group for each SOC and PT ([Table 12](#)).
- The number and proportion of subjects reporting at least one AE, summarized by Dose Group, SOC, PT, maximum severity, and relatedness ([Table 13](#)).
- By Dose Group, bar charts of proportions of subjects with related serious and non-serious AEs by maximum severity and SOC. This figure describes the number of subjects with an event (each subject counted once per SOC) ([Figure 17](#)).

- By Dose Group, bar charts of numbers of related serious and non-serious AEs by severity and SOC. This figure describes the total number of occurrences of each event, including multiple occurrences per subject ([Figure 18](#)).

## 7.4. Deaths, Serious Adverse Events and other Significant Adverse Events

Individual data listings of deaths and other SAEs will be provided ([Table 14](#)).

## 7.5. Pregnancies

An individual data listing of pregnancy reports will be provided if a pregnancy occurs pose-dosing ([Listing 25](#), [Listing 26](#), [Listing 27](#), [Listing 28](#), [Listing 29](#)). Contraceptive method will be listed in [Listing 30](#).

## 7.6. Clinical Laboratory Evaluations

If the time of sample collection for clinical laboratory evaluations was prior to 23DEC2019, then grading will follow toxicity grade criteria from protocol v3.0. If the time of sample collection was on or after 23DEC2019, then grading will follow toxicity grade criteria from protocol v4.0. Note that toxicity ranges from protocol v4.0 through v6.0 were identical.

- CHEM: Total cholesterol, low-density lipoprotein cholesterol, high-density lipoprotein cholesterol, and triglycerides were removed from clinical lab collection after protocol v3.0.
- COAG: Prothrombin time and activated PTT toxicity ranges were updated after protocol v3.0.
- UA: Blood in urine (microscopic) toxicity ranges were updated after protocol v3.0.

All screening and safety laboratory results will be listed in [Listing 11](#) (CHEM), [Listing 12](#) (HEM), [Listing 13](#) (COAG), [Listing 14](#) (UA), [Listing 15](#) (serology), [Listing 16](#) (urine toxicity), and [Listing 17](#) (pregnancy test). Abnormal laboratory results (laboratory results outside of the normal range on time of collection) will be listed in [Table 16](#) (CHEM), [Table 17](#) (HEM), [Table 18](#) (COAG), and [Table 19](#) (UA).

Laboratory results will be summarized in tables and figures:

- Tabularly, by parameter, Dose Group, time point, and toxicity grade (including maximum severity post-baseline). Summaries will be presented in [Table 20](#) (CHEM), [Table 22](#) (HEM), [Table 24](#) (COAG), and [Table 26](#) (UA). When calculating the proportions of subjects with a laboratory toxicity, each subject will only be counted once per toxicity grade and any repetitions of laboratory toxicities within a subject will be ignored, and the event will be reported according to the worst severity recorded. Parameters with no specified toxicity ranges listed in protocol will be excluded from this summary.
- Tabularly, by summary statistics for change from baseline, reported by parameter, Dose Group, and time point. Summaries will be presented in [Table 21](#) (CHEM), [Table 23](#) (HEM), and [Table 25](#) (COAG).
- Graphically, using box plots of change from baseline by parameter, Dose Group, and time point.
  - CHEM: Beginning at [Figure 19](#) and continuing through [Figure 35](#).
  - HEM: Beginning at [Figure 36](#) and continuing through [Figure 45](#).
  - COAG: [Figure 46](#), [Figure 47](#), and [Figure 48](#).

The following laboratory parameters will be presented (in order):

- Chemistry (CHEM): sodium, potassium, calcium, phosphorus, chloride, total carbon dioxide, glucose, blood urea nitrogen, creatinine, total cholesterol, low-density lipoprotein cholesterol, high-density lipoprotein cholesterol, triglycerides, total protein, albumin, aspartate aminotransferase (AST), alanine aminotransferase (ALT), alkaline phosphatase, total bilirubin, direct bilirubin, creatine phosphokinase. Total cholesterol, low-density lipoprotein cholesterol, high-density lipoprotein cholesterol, and triglycerides parameters were removed after Protocol v3.0. Only Cohort 1 subjects have results for the specified parameters. Due to limited number of subjects with available results, total cholesterol, low-density lipoprotein cholesterol, high-density lipoprotein cholesterol, and triglycerides will only be presented in [Table 21](#) and [Listing 11](#) and will be excluded from the change from baseline figures.
- Hematology (HEM): hemoglobin, hematocrit, RBC count, WBC count, neutrophil count, lymphocyte count, monocyte count, eosinophil count, basophil count, platelet count.
- Coagulation (COAG): prothrombin time, activated PTT, INR
- Urinalysis (UA): protein, glucose, occult blood.

By protocol, microscopic evaluation of urine or complete urinalysis is only performed if dipstick urinalysis is positive for blood. If complete UA or microscopic results were obtained in the absence of an abnormal dipstick result (or without dipstick tests being done), results of the complete UA or microscopy will still be summarized. Results determined using both methods will be listed. In tables, dipstick results will be presented prior to complete UA or microscopy results.

Laboratory parameters that have grading criteria for both decreases (result lower than normal range) and increases (result higher than normal range) will be summarized separately by direction of change. For example, sodium will be summarized separately as “Sodium, Decrease” and “Sodium, Increase.”

In tables summarizing toxicity grading, maximum severity observed after dosing will be summarized (max severity post-baseline, including unscheduled visits) for each parameter. Results of maximum severity for “Any Parameter” will be included for all clinical laboratory results. For “Any Parameter” results, the maximum severity across all laboratory parameters in the respective category is summarized by time point.

Unscheduled clinical laboratory evaluations will be listed, but excluded from tabular and graphical summaries, except when calculating the maximum severity post-baseline. Any pre-existing abnormal lab results at screening will be graded and presented in listings but will not be reported as an AE unless they are treatment-emergent (i.e. it worsens after dosing, meaning for continuous parameters that an increase toxicity can only be assigned if the result is numerically higher than baseline and a decrease toxicity can only be assigned if the result is numerically lower than baseline.)

## 7.7. Vital Signs and Physical Evaluations

All VS measurements will be presented in [Listing 18](#).

VS will be summarized in tables and figures:

- Tabularly, by parameter, Dose Group, time point, and toxicity grade (including maximum severity post-baseline). Respiratory rate measurements are not graded, and so will not be included in this summary. ([Table 27](#)).
- Tabularly, by summary statistics for change from baseline, reported by parameter, Dose Group, and time point. ([Table 28](#)).

- Graphically, using box plots of change from baseline by parameter, Dose Group, and time point. ([Figure 49](#), [Figure 50](#), [Figure 51](#), [Figure 52](#), [Figure 53](#)).

The following parameters will be reported (in order): systolic blood pressure (BP), diastolic BP, heart rate, respiratory rate, and temperature.

VS parameters that have grading criteria for both decreases (result lower than normal range) and increases (result higher than normal range) will be summarized separately by direction of change. For example, systolic blood pressure will be summarized separately as “Systolic Blood Pressure, Decrease” and “Systolic Blood Pressure, Increase.”

In tables summarizing toxicity grading, maximum severity observed after dosing will be summarized for each parameter. Results of maximum severity for “Any Parameter” will also be included. For “Any Parameter” results, the maximum severity across all vital sign parameters is summarized by time point.

Unscheduled VS measurements will be listed, but excluded from tabular and graphical summaries, except when calculating the maximum severity post-baseline. Baseline for height, weight, and BMI will be the measurement taken at Screening Visit, baseline for the rest of the VS parameters is defined as the last vital sign parameter taken before dosing on Day 1 (including any repeats). Repeated VS due to clinic error or technical problem will be used for all analyses instead of the original vital sign result. Additional measurements taken as follow-up for safety will be included in listings and in computing maximum severity post baseline, but not as separate time points in summary tables. For repeats that were done due to delayed dosing, the last measurement prior to dosing will be considered as baseline for that subject.

Abnormal PE findings will be listed in [Listing 19](#).

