7.1.5 Vital Signs

Vital signs (body temperature, heart rate, respiration rate, and blood pressure) will be obtained at times specified in [Appendix A](#). Vital signs will be measured after resting at least 5 minutes. The pre-dose vital signs on days of dosing will be measured within 60 minutes of study drug dosing; Day 1 post-dose vital signs measurements should be taken within \pm 5 minutes of the 15-minute post-dose timepoint and within \pm 10 minutes for additional post-dose timepoints. Other vital signs during the inpatient stay will be taken within \pm 30 minutes of the nominal timepoint. For outpatient visits, vital signs will be measured within the visit window.

Day 1 post-dose timepoints for vital sign measurements for the IV portion of Part 3 will be based on the start of infusion.

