10.5.2 Clinical Safety Labs, Vital Signs, and Electrocardiograms

Baseline for clinical safety labs, vital signs, and ECGs will be defined as the last result obtained before the dose of study product. For crossover data, there will be a separate baseline for each treatment. Changes from baseline for clinical safety labs, vital signs, and ECGs results will be summarized by dose group and time point. Clinical safety labs and vital signs will be graded ([Appendix B](#)) and summarized by severity, group, and visit. Rules for analyzing replicates for a safety time point (labs, vital signs, ECG), if obtained, will be described in the SAP.

Treatment-emergent abnormal laboratory test results will be identified. Treatment-emergent abnormal laboratory tests are tests for which the result was not graded as mild or worse at baseline but graded as mild or worse after dosing. Laboratory tests graded as mild at baseline, but moderate or worse any time after dosing will also be regarded as treatment-emergent abnormal laboratory test results.

ECG measurements will include heart rate, RR interval, QT interval, QTcF interval, PR interval, and QRS duration. Baseline for ECG measurements is defined per protocol as the value pre-dosing on Day 1 (or pre-dosing on Day 21 for period 2 of Part 3). Change from baseline will be summarized descriptively by regimen at each scheduled evaluation. QTc results will be summarized categorically according to the ICH Guideline E14 “Clinical Evaluation of QT/QTc Interval Prolongation and Proarrhythmic Potential for Non-Antiarrhythmic Drugs” (October 2005):

- QTcF >450 ms, males only
- QTcF >470 ms, females only
- QTcF >480 ms
- QTcF >500 ms
- QTcF increases from baseline by at least 30 ms but less than 60 ms
- QTcF increases from baseline by at least 60 ms

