Appendix B. TOXICITY TABLE

Clinical Adverse Events			
VITAL SIGNS	Mild (Grade 1)	Moderate (Grade 2)	Severe Grade 3
Fever - °C	38.0-38.4	38.5-38.9	>38.9
Tachycardia - bpm	101-115	116-130	>130 or ventricular dysrhythmias
Bradycardia – bpm • Baseline ≥60 OR, if Baseline <60	• 50-54 OR, if Baseline <60, • 45-50	• 45-49 OR, if baseline <60, • 40-44	• <45 OR, if baseline <60 • <40
Hypertension (systolic) - mmHg	141-150	151-160	>160
Hypertension (diastolic) - mmHg	91-95	96-100	>100
Hypotension (systolic) - mmHg	85-89	80-84	<80
Tachypnea – breaths per min	23-25	26-30	>30
CARDIOVASCULAR	Mild (Grade 1)	Moderate (Grade 2)	Severe Grade 3)
Arrhythmia		Asymptomatic; transient signs; no medical intervention required	Recurrent/persistent; symptomatic medical intervention required
Hemorrhage, Blood Loss	Estimated blood loss ≤100 mL	Estimated blood loss >100 mL; no transfusion required	Transfusion required

QTc (Fridericia's correction) ¹	Asymptomatic, QTc interval 450-479 msec	Asymptomatic; QTc interval 480 to 499 msec OR Increase in interval 30-59 msec above baseline	Asymptomatic; QTc interval \geq 500 msec OR Increase in interval \geq 60 msec above baseline
PR Interval (prolonged) ¹	PR interval 0.21-0.25 sec	PR interval >0.25	Type II 2 nd degree AV block OR Ventricular pause >3.0 sec
RESPIRATORY	Mild (Grade 1)	Moderate (Grade 2)	Severe (Grade 3)
Cough	Transient; no treatment	Persistent cough	Interferes with daily activities
Bronchospasm, Acute	Transient; no treatment; FEV1 71-80% of predicted peak flow	Requires medical intervention; normalizes with bronchodilator; FEV1 60-70% of predicted peak flow	No normalization with bronchodilator; FEV1 $<60\%$ of predicted peak flow
Dyspnea	Does not interfere with usual and social activities	Interferes with usual and social activities; no treatment	Prevents daily and usual social activity OR requires treatment
GASTROINTESTINAL	Mild (Grade 1)	Moderate (Grade 2)	Severe (Grade 3)
Nausea	No interference with activity	Some interference with activity	Prevents daily activities
Vomiting	No interference with activity OR 1-2 episodes/24 hours	Some interference with activity OR >2 episodes/24 hours	Prevents daily activity OR requires IV hydration OR requires medical intervention

¹Inclusion dependent upon protocol requirements.

Diarrhea	2-3 loose or watery stools or <400 g/24 hours	4-5 loose or watery stools or 400-800 g/24 hours	≥6 loose or watery stools or >800g/24 hours OR requires IV hydration OR requires medical intervention

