## 10. TECHNICAL DETAILS

SAS version 9.4 or above or R versions 3.2 or above will be used to generate tables, figures, and listings. PK parameters will be estimated through an NCA using Phoenix® WinNonlin® version 8.2 or later (Certara, Princeton, NJ).

---

**11. SUMMARY OF CHANGES IN THE CONDUCT OF THE STUDY OR  
PLANNED ANALYSES**

The sponsor terminated the study on 27APR2020 due to safety concerns. No subjects were enrolled into SAD Cohort 3 (30 mg) and above, any MAD cohort, or the BA cohort. Only SAD 1 mg and SAD 10 mg Dose Groups will be included in the final safety analysis and SAD 10 mg Dose Group will be included in the final PK analysis.

---

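### SAP 7.7 leaves respiratory rate out of the graded vital-sign table as ungraded, but protocol Appendix B grades tachypnea

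*SAP*

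**What the plan says.** SAP 7.7 plans three kinds of vital-sign display: toxicity grades by dose group and time point (Table 27), change from baseline (Table 28), and box plots of change (Figures 49 to 53). It names five parameters: systolic pressure, diastolic pressure, heart rate, respiratory rate and temperature. For Table 27 only, it adds: "Respiratory rate measurements are not graded, and so will not be included in this summary". For the *Any Parameter* rows of the same table it says that "the maximum severity across all vital sign parameters is summarized by time point".

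The protocol treats respiratory rate as a vital sign like the others. Section 7.1.5 reads: "Vital signs (body temperature, heart rate, respiration rate, and blood pressure) will be obtained at times specified in" Appendix A. The vital-signs part of Appendix B has a row labelled "Tachypnea – breaths per min", with ranges for mild, moderate and severe. On analysis, protocol 10.5.2 says: "Clinical safety labs and vital signs will be graded", with reference to Appendix B, and asks for the grades to be tabulated by severity, group and visit.

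The SAP adopts that scale in its own section 7: "Toxicity grading scales for adverse events, solicited reactogenicity symptoms, safety labs, VS, and ECG are provided in the protocol v6.0".

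**The concern.** The SAP gives a factual reason for the omission, and the grading table that the SAP itself adopts contradicts it. This is not presented as a deliberate departure from the protocol. A programmer who follows SAP 7.7 would produce a graded table that lacks a summary the protocol requires, and a reader of the report would conclude that the protocol has no grade for respiratory rate.

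Vital signs are part of the primary safety outcome (protocol 3.3.1). Table 27 is the only planned display that summarizes graded vital signs by dose group and time point. Two things are at stake: the missing respiratory-rate block, and an *Any Parameter* summary that is described as covering every vital sign but would not.

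**Working it through.** The plan gives no figure to reproduce, so the check compares the texts and counts what is lost.

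**1. Is respiratory rate graded?** The parameters listed in SAP 7.7, set against protocol Appendix B:

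| Parameter | Abnormality graded in Appendix B | In Table 27 under SAP 7.7 |
|---|---|---|
| Systolic pressure | hypertension, hypotension | yes |
| Diastolic pressure | hypertension | yes |
| Heart rate | tachycardia, bradycardia | yes |
| Temperature | fever | yes |
| Respiratory rate | tachypnea: 23-25 mild, 26-30 moderate, >30 severe | no |

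All 5 parameters are graded and Table 27 keeps 4. By abnormality, Appendix B grades 2 + 1 + 2 + 1 + 1 = 7 and Table 27 covers 6.

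**2. Does anything else in the documents explain the omission?**

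- SAP 7.6 has a rule on which protocol version supplies the grades, but it begins "If the time of sample collection for clinical laboratory evaluations was prior to 23DEC2019". It concerns laboratory samples only.
- SAP section 11, the summary of changes, records only the early termination (for example "No subjects were enrolled into SAD Cohort 3 (30 mg) and above, any MAD cohort, or the BA cohort"). It does not mention vital-sign grading.
- A difference in protocol version is unlikely. The protocol's chemistry panel lacks the lipids that SAP 7.6 says were removed after v3.0. SAP 7.8 cites v6.0 section 10.5.2 for the QTcF categories, and those categories stand in the protocol's 10.5.2.

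**3. What happens to *Any Parameter*?** The Table 27 shell does not list which parameters enter these rows, so this step is an inference. A parameter handled as ungraded has no severity to contribute to a maximum, so programming the text as written leaves tachypnea out.

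**4. Size of the missing block.** The shell has 10 rows per dose group: baseline, maximum post-baseline, Day 1 at 15 min, 1 h and 2 h, Days 2, 4, 7 and 14, and the final visit. There are 4 dose groups. The implementation note reduces a parameter to its maximum-severity row when no graded post-baseline event occurs.

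- At least one graded event: 4 × 10 = 40 rows.
- None: 4 × 1 = 4 rows.

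**5. Illustrative effect on *Any Parameter*.** Assume that Cohorts 1 and 2 filled as planned in protocol 3.1.1.1 and that everyone has post-dose vital signs. The documents do not give actual enrolment. Active subjects are 3 (1 mg) and 6 (10 mg), so 3 + 6 = 9 for any dose; placebo is 1 + 2 = 3. For one subject whose only graded vital sign is tachypnea, the maximum-severity row shifts by 1/N:

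| Dose group | N | Shift (percentage points) |
|---|---|---|
| SAD 1 mg | 3 | 1/3 = 33 |
| SAD 10 mg | 6 | 1/6 = 17 |
| SAD Any Dose | 9 | 1/9 = 11 |
| Placebo | 3 | 1/3 = 33 |

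If that subject has another vital sign of equal or worse grade, the shift in that row is 0.

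**The case against.** The best reply accepts the contradiction and argues that it hardly matters. The trial tests no hypothesis, the study stopped after two small cohorts, and the report is abbreviated. Respiratory-rate values stay in Listing 18, and changes from baseline stay in Table 28 and Figure 52. Appendix B files tachypnea under clinical adverse events, and protocol 8.1.1 has a recording rule for vital-sign AEs. Tachypnea reported as an AE would therefore reach Table 13 by dose group and severity. The percentage shifts assume full enrolment, although Cohort 2 dosed two sentinels at least 4 weeks before the rest, and no frequency of isolated tachypnea is given. Finally, protocol section 10 lets the SAP depart from the protocol analysis if the SAP describes the departure.

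Much of this stands, and it limits the consequence. The AE tables and the listing soften the loss but do not replace Table 27. They give no layout by time point and no baseline row, and they do not summarize graded readings that were not reported as AEs. Listing 18 asks for severity on abnormal results, but calling respiratory rate ungraded leaves it unclear whether that instruction applies. The percentage shifts are illustrations only and carry no weight in deciding whether the text is wrong. As for a permitted departure, SAP 7.7 states the omission openly but rests it on a mistaken fact; it neither identifies nor justifies a change from protocol 10.5.2.

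**Conclusion.** The concern holds. The reason SAP 7.7 gives is contradicted by the grading table the SAP adopts, and the resulting Table 27 falls short of protocol 10.5.2. One of five vital-sign parameters is missing, a block of 4 to 40 rows. By inference, tachypnea is also missing from the *Any Parameter* rows. The blood pressure, heart rate and temperature rows are unaffected.

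The consequence is modest: an incomplete descriptive table for part of the primary safety outcome. No estimate, test or escalation decision changes. Any numerical effect depends on whether a subject had graded tachypnea with no other vital sign of equal or worse grade, which the documents cannot tell us. The 11 to 33 point shifts also rest on planned cohort sizes. The point should still be corrected, because the error is plain and costs little to remove.

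**What to change.** In SAP 7.7, delete the sentence that excludes respiratory rate. Add a respiratory-rate (tachypnea) block to Table 27 using the ranges already in Appendix B. Only increases are graded, so the block needs no split by direction. State that it counts toward the *Any Parameter* rows, both by time point and for maximum severity post-baseline. Confirm that the severity instruction in Listing 18 applies to respiratory rate.

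If the sponsor prefers to keep the exclusion, SAP section 11 should record it as a departure from protocol 10.5.2 with a genuine reason, and the present reason should be removed.

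The cost is one sentence and one extra block in an existing table. The data are already collected and the ranges already exist.
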